### **9 STUDY OBJECTIVES**

#### **9.1 Primary Objective**

The primary objective of the study is:

- To evaluate the long-term safety and tolerability of amifampridine in patients with SMA Type 3.

#### **9.2 Secondary Objective**

The secondary objective of the study is:

- To assess the clinical efficacy of amifampridine phosphate over time in patients with SMA Type 3 based on changes in QoL.

 Catalyst <small>pharmaceuticals</small>	SMA-002	Page 18
---	---------	---------

## 10 INVESTIGATIONAL PLAN

### 10.1 Overall Study Design and Plan

This open label outpatient extension study is designed to evaluate the long-term safety, tolerability of amifampridine in patients diagnosed with SMA Type 3. In addition, evaluation of the effects of amifampridine on the QoL will be made. The study will enroll those patients who have completed the SMA-001 study and after all final evaluations for that study have been completed, or those who demonstrated benefit after completing the dose titration period but failed to meet the randomization criteria on Day 0 of SMA-001.

The duration of participation for each patient is expected to be at least 12 months as patients may continue in the study until amifampridine is approved by Regulatory Agencies or the clinical development of amifampridine is terminated for this indication. In addition to amifampridine, patients will continue to receive previous concomitant medications, as needed.

After a new informed consent is signed and inclusion / exclusion criteria for the current protocol are satisfied, eligible patients will be given the optimal dose and dosing schedule that was identified in the Run-in Period from Protocol SMA-001.

The findings from the physical exam (including vital signs, weight); 12-lead ECG; clinical laboratory test results (including pregnancy testing) and any ongoing adverse events will be used as the baseline for the Long-Term safety evaluation.

The efficacy measurement is QoL which will be completed every 3 or 6 months. Safety and tolerability assessments will be made every 3 or 6 months or more frequently at the discretion of the Investigator. The study will continue until amifampridine is approved by Regulatory Agencies or until development of the product for this indication is halted. The Investigator may alter the dose and dosing frequency during the Long-Term Study as well as schedule additional clinic visits for any reason.

Patients will be seen in the clinic at the end of Months 3, 6, 9, 12, 15, 21 and 27 as detailed in the Schedule of Assessments in [Table 1](#) and Section 13. In between the 3-or 6-month visits, patients may also have telephone/video contact with the site, or unscheduled visits, if needed.

Any unused medication must be returned to the clinic at each visit for drug accountability, and an additional supply will be dispensed.

The study will be completed when amifampridine is approved by Regulatory Agencies for Spinal Muscular Atrophy or the clinical development of amifampridine is terminated for this indication.

**Table 1 Schedule of Events**

Study Assessment or Event	Screening and Enrollment*	End of Study Month ± 1 week							
		3	6	9	12	15	21	27	EoS g
Informed consent a	x								
Inclusion/Exclusion Criteria	x								
Complete physical exam b	x	x	x	x	x	x	x	x	x
Vital signs	x	x	x	x	x	x	x	x	x
12-Lead ECG	x	x	x	x	x	x	x	x	x
Clinical laboratory tests c	x	x	x	x	x	x	x	x	x
Pregnancy test d	x	x	x	x	x	x	x	x	x
Amifampridine Treatment		x	x	x	x	x	x	x	
QoL	x	x	x	x	x	x	x	x	x
Dispense IP e	x	x	x	x	x	x	x		
IP accountability		x	x	x	x	x	x	x	x
Adverse events/SAEs f	x	x	x	x	x	x	x	x	x
Concomitant medications	x	x	x	x	x	x	x	x	x

EoS= End of Study is the patients last visit to the site and discontinuation of study medication; IP=investigational product; QoL=quality of life; SAE=serious adverse event.

a Informed consent must be obtained before any study procedures are performed.

b Complete physical examination includes evaluation of all major body systems, including weight at all visits (Section 10.6.6).

c Clinical laboratory tests include serum chemistry, hematology, and urinalysis.

d Urine pregnancy tests will be obtained from female patients of childbearing potential.

e Pharmacist will dispense sufficient amount of medication until the next clinic visit. All unused medication must be returned to the clinic for drug accountability.

f SAE reporting commences after informed consent is signed. Non-serious adverse event reporting commences after the first dose of study drug for the current Long-Term Study.

g EoS or early termination visit if the last visit does not coincide the scheduled 3- or 6-month visit.

\*These data may be obtained from Study SMA-001. If data not available, then the assessment should be repeated.

	SMA-002	Page 20
---	---------	---------

## 10.2 Selection of Study Population

Patients who complete Protocol SMA-001 or who have demonstrated benefit after completing the dose titration period but failed to meet randomization criteria for SMA-001 and who meet the inclusion and exclusion criteria for participation in the current study will be eligible.

### 10.2.1 Inclusion Criteria

Individuals eligible to participate in this study must meet all the following inclusion criteria:

1. Participated in the SMA-001 study
2. Willing and able to provide written informed consent after the nature of the study has been explained and before the start of any research-related procedures.
3. Female patients of childbearing potential defined according to the Clinical Trial Facilitation Group - CTFG guidelines\* must have a negative pregnancy test (urine human chorionic gonadotropin [HCG] at the end of SMA-001 study); and must practice an effective, reliable contraceptive regimen during the study and for up to 30 days following discontinuation of treatment.
4. Ability to participate in the study based on overall health of the patient and disease prognosis, as applicable, in the opinion of the Investigator; and able to comply with all requirements of the protocol, including completion of study questionnaires.

\* According to CTFG guidelines a woman is considered of childbearing potential, i.e. fertile, following menarche and until becoming post-menopausal unless permanently sterile.

Permanent sterilisation methods include hysterectomy, bilateral salpingectomy and bilateral oophorectomy. A postmenopausal state is defined as no menses for 12 months without an alternative medical cause.

### 10.2.2 Exclusion Criteria

Individuals who met any of the exclusion criteria in the original protocol or those listed below are not eligible to participate in the study:

1. Epilepsy and currently on medication.
2. Uncontrolled asthma.
3. Concomitant use with sultopride.
4. Concomitant use with medicinal products with a narrow therapeutic window.
5. Clinically significant abnormalities in 12 lead ECG, in the opinion of the Investigator.

	SMA-002	Page 21
---	---------	---------

6. Breastfeeding or pregnant at Screening or planning to become pregnant at any time during the study.
7. Intolerable amifampridine-related side effects
8. Treatment with an investigational drug (other than amifampridine) or device while participating in this study.
9. Any medical condition that, in the opinion of the Investigator, might interfere with the patient's participation in the study, poses an added risk for the patient, or confound the assessment of the patient.
10. History of drug allergy to any pyridine-containing substances or any amifampridine excipient(s).

#### **10.2.3 Removal of Patients from Treatment or Assessment**

Patients may withdraw their consent to participate in the study or to receive treatment with IP at any time without prejudice. The Investigator must withdraw from the study or from treatment with IP any patient who requests to be withdrawn. A patient's participation in the study or treatment with IP may be discontinued at any time at the discretion of the Investigator and in accordance with his or her clinical judgment.

Catalyst must be notified of all patient withdrawals from the study or from treatment with IP as soon as possible. Catalyst also reserves the right to discontinue the study at any time for either clinical or administrative reasons and to discontinue participation by an individual Investigator or site for poor enrollment or noncompliance.

Reasons for which the Investigator or Catalyst may withdraw a patient from the study treatment include, but are not limited to, the following:

- Patient experiences a serious or intolerable AE;
- Patient requires medication prohibited by the protocol;
- Patient becomes pregnant (refer to Section 11.4 for details on the reporting procedures to follow in the event of pregnancy);
- Patient does not adhere to study requirements specified in the protocol;
- Patient was erroneously admitted into the study or does not meet inclusion criteria;
- Patient is lost to follow-up.

If a patient fails to return for scheduled visits, a documented effort must be made to determine the reason. If the patient cannot be reached by telephone, a certified letter should

	SMA-002	Page 22
---	---------	---------

be sent to the patient requesting contact with the Investigator. This information should be recorded in the study records.

The Investigator or designee must explain to each patient, before enrollment into the study, that for evaluation of study results, the patient's protected health information obtained during the study may be shared with Catalyst, regulatory agencies, and IRB/IEC/REB. It is the Investigator's (or designee's) responsibility to obtain written permission to use protected health information, per country-specific regulations, from each patient. If permission to use protected health information is withdrawn, it is the Investigator's responsibility to obtain a written request, to ensure that no further data will be collected from the patient and the patient will be removed from the study.

#### **10.2.4 Patient Identification**

Each patient will be assigned a unique patient identifier (2 digit for the site and 2 digit for each patient enrolled). This unique identifier will be on all CRF pages.

### **10.3 Treatments**

#### **10.3.1 Treatments Administered**

Catalyst or its designee will provide the study site with a supply of Investigational product: amifampridine tablets 10 mg at various intervals sufficient for the completion of the study.

[figure not shown]
Amifampridine will be provided in round, white-scored tablets and containing amifampridine phosphate formulated to be the equivalent of 10 mg amifampridine base per tablet. The product will be provided in bottles of bulk tablets to the Catalyst designee who will dispense to the site an amount for each portion of the study, in a patient-specific labeled bottle.

#### **10.3.2 Identity of Investigational Product**

The chemical name of amifampridine phosphate is:

- 3,4-pyridinediamine, phosphate (1:1) diamino-3,4-pyridine, phosphate salt
- 3,4-diaminopyridine phosphate

The chemical structure is provided in Figure 1.

**Figure 1. Chemical Structure of Amifampridine Phosphate**

#### **10.3.2.1 Product Characteristics and Labeling**

Drug product is formulated as a phosphate salt of amifampridine. Tablets were developed to provide the equivalent of 10 mg of amifampridine base for oral administration. Each tablet contains amifampridine phosphate, microcrystalline cellulose, colloidal anhydrous silica, and calcium stearate. The bottles of tablets are labeled “Amifampridine Phosphate Tablets, 10 mg.”

The tablets are to be dispensed by the Catalyst designee into suitably sized pharmacy containers for patient use. Each bottle provided to patients will be labeled to include the compound name, site number, patient ID number, date dispensed, storage instructions, the statement ‘Caution – New Drug – Limited to investigational use’, trial number, manufacturer name and address, and area for instructions for use. Regional label requirements and translations should be used in accordance with local regulations.

#### **10.3.2.2 Storage**

All IP must be stored under the conditions specified, 20-25° Celsius (C) (excursions between 15-30° may be permitted) and in a secure area accessible only to the pharmacist. All IP must be stored and inventoried, and the inventories must be carefully and accurately documented according to applicable national and local regulations, ICH GCP, and study procedures.

#### **10.3.3 Directions for Administration**

All doses of study drug will be taken as outpatients. Study drug should be taken every day at approximately the same time, on empty stomach or with small amount of food (crackers) since food significantly delays the absorption of the drug and will slow onset of action, at the dose and frequency instructed by Investigator.

The dose of amifampridine will be based on optimal neuromuscular benefit determined from the Run-in Period from SMA-001 or may be modified as the discretion of the Investigator.

	SMA-002	Page 24
---	---------	---------

The maximum single dose is 20 mg. The dose range for patients 6 to 16 years of age is 15 to 60 mg and for those 17 years and older, the range is from 30 to 80 mg daily. The daily dose of amifampridine can be adjusted during this long-term at the discretion of the Investigator.

#### **10.3.4 Method of Assigning Patients to Treatment Groups**

All patients will receive open label amifampridine. Details on study drug preparation, dispensing medication will be included in the Pharmacy Manual.

#### **10.3.5 Selection of Doses Used in the Study**

Initially, the daily amifampridine dose will be the one that was determined at the end of the Run-in Period from SMA-001. The usual range is 20 to 80 mg total daily dose, given in 3 or 4 divided doses, with no single dose >20 mg. Safety of a single maximum dose of 20 mg is based on completed animal and *in vitro* pharmacology, PK, and toxicology studies.

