### 3      SYNOPSIS

TITLE OF STUDY:	Long Term Safety Study of Amifampridine Phosphate in Ambulatory Patients with Spinal Muscular Atrophy (SMA) Type 3
PROTOCOL NUMBER:	SMA-002
STUDY SITES:	Up to 3 sites
PHASE OF DEVELOPMENT:	Phase 2a
STUDY RATIONALE:	
The purpose of this study is to evaluate the long-term safety and tolerability of amifampridine phosphate in ambulatory patients with SMA Type 3 who completed Protocol SMA-001 or, who benefit from the medication but were not meet the criteria enter the double-blind portion of SMA-001.

OBJECTIVES:	
Primary
 
 
• To characterize the long-term safety and tolerability of amifampridine phosphate in patients SMA Type 3
 

Secondary	
 
• To assess the clinical efficacy of amifampridine phosphate over time in patients with SMA Type 3 based on changes in quality of life (QoL)
 

STUDY DESIGN AND PLAN:	
This is a long-term extension study for patients who participated in Protocol SMA-001 where the efficacy and safety of amifampridine was evaluated, in ambulatory patients with SMA Type 3. The planned duration of participation for each patient is approximately 2 years (i.e. until amifampridine is approved by Regulatory Agencies for the treatment of SMA Type 3 or the development program is discontinued for this indication).
 
All patients who have completed study SMA-001 and sign an informed consent may enroll in the long-term study. Those patients who demonstrated benefit after completing the dose titration period but failed to meet the randomization criteria on Day 0 (end of the Run-in period for SMA-001 may also be eligible for this study. The evaluations at the end of participation in Study SMA-001 will as baseline for the Long-Term study.

The optimal dose and schedule for amifampridine from the end of the Run-in Period from Study SMA-001 will initially be used for each patient. The Investigator may adjust the dose of amifampridine during the course of this trial, in order to optimize neuromuscular benefit for the patient. Clinic visits for safety assessment and for evaluation of QoL will be made at Months 3, 6, 9, 12, 15, 21 and 27. Additional visits may occur at the discretion of the Investigator.

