**INVESTIGATIONAL PRODUCT(S), DOSE, ROUTE, AND REGIMEN:**

The investigational product (IP) is amifampridine tablets 10 mg, and it will be provided in round, white-scored tablets, containing amifampridine phosphate formulated to be the equivalent of 10 mg amifampridine base per tablet. Dosing is up to 80 mg/day in 3 or 4 divided doses.

The investigational product will be provided by Catalyst Pharmaceuticals, Inc., [name], United States.

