10.10.2 Duration of Treatment and Compliance

Duration of treatment will be summarized for the SAF analysis set.

The duration of treatment is the (*date of the last study drug dose intake* minus the *date of administration of the first dose of study drug*) +1.

Compliance is 100%*(Number consumed)/(Number prescribed). “Number consumed” is from Study Drug Accountability and “Number prescribed” is number of tablets to have been taken daily duration. Compliance will be summarized for the SAF analysis set.

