xxx	xxx	xxx	xxx	xxx	xxx.x
xxx	xxx	xxx	xxx	xxx	xxx.x

Source: [program name].sas, Run on ddmmmyyyy.

Programming Notes: Sort by site and patient number. Number of Tablets Dispensed, Number of Tablets Used, and Treatment Duration are totals from next listing. Compliance is determined from these totals.

Listing 16.2.5.2.2 Study Drug Accountability

Site	Patient	Date of IP dispensing	Visit (1)	Box kit number	No. of tablets dispensed	Start date of period covered with this box	End date of period covered with this box	No. of tablets returned	No. of tablets used	No. of tablets lost	Total tablets used, returned and lost (calculated)	Divided in the following frequency (2)	Total daily dose (mg) (3)
xxx	xxx	DDMMYYYY	xx	xx	xx	DDMMYYYY	DDMMYYYY	xx	xx	xx	xx	xx	xx
		DDMMYYYY	xx	xx	xx	DDMMYYYY	DDMMYYYY	xx	xx	xx	xx	xx	xx
		DDMMYYYY	xx	xx	xx	DDMMYYYY	DDMMYYYY	xx	xx	xx	xx	xx	xx
xxx	xxx	DDMMYYYY	xx	xx	xx	DDMMYYYY	DDMMYYYY	xx	xx	xx	xx	xx	xx
		DDMMYYYY	xx	xx	xx	DDMMYYYY	DDMMYYYY	xx	xx	xx	xx	xx	xx
		DDMMYYYY	xx	xx	xx	DDMMYYYY	DDMMYYYY	xx	xx	xx	xx	xx	xx

(1) Visit: Screening, End of study month 3, End of study month 6, End of study month 9, End of study month 12, End of study month 15, End of study month 21, End of study month 27, EoS, Extra visit

(2) Divided in the following frequency: 3 times per day, 4 times per day

(3) Total Daily Dose (mg): 5, 10, 15, 20, 25, 30, 35, 40, 45, 50, 55, 60, 65, 70, 75, 80

Source: [program name].sas, Run on ddmmmyyyy.

Programming Note: Sort by site and patient number and date of IP dispensing.

Listing 16.2.6.1. Quality of Life (QoL): Type of Questionnaire

Site	Patient	Visit	QoL questionnaire performed?	If No, specify reason	Date of test performed	Time of test performed (hh:mm)	Type of questionnaire (1)
xxx	xxx	Screening	xxx		DDMMYYYY	xx:xx	xxxxxxxxxx
		Month 3	xxx		DDMMYYYY	xx:xx	xxxxxxxxxx
		Month 6	xxx		DDMMYYYY	xx:xx	xxxxxxxxxx
		Month 9	No	xxxxxxxxxx	DDMMYYYY	xx:xx	xxxxxxxxxx
		...	xxx		DDMMYYYY	xx:xx	xxxxxxxxxx
		EOS	xxx		DDMMYYYY	xx:xx	xxxxxxxxxx
xxx	xxx	Screening	xxx		DDMMYYYY	xx:xx	xxxxxxxxxx
		Month 3	xxx		DDMMYYYY	xx:xx	xxxxxxxxxx
		Month 6	xxx		DDMMYYYY	xx:xx	xxxxxxxxxx
		Month 9	xxx		DDMMYYYY	xx:xx	xxxxxxxxxx
		...	xxx		DDMMYYYY	xx:xx	xxxxxxxxxx
		EOS	xxx		DDMMYYYY	xx:xx	xxxxxxxxxx

(1) Type of questionnaire: PEDSQL Parent Report for Young Child (ages 5-7), PEDSQL Parent Report for Child (ages 8-12), PEDSQL teen (ages 13-18), INQOL (ages > 18)

Source: [program name].sas, Run on ddmmmyyyy.

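### Protocol 10.3.5 gives one 20–80 mg/day range for all ages, which conflicts with the age-specific ranges in Protocol 10.3.3 and SAP 5.3

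*Protocol*

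**What the plan says.** The daily dose is described in four places.

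- Protocol 10.3.5 (Selection of Doses): "The usual range is 20 to 80 mg total daily dose, given in 3 or 4 divided doses, with no single dose >20 mg". No age is mentioned.
- Protocol 10.3.3 (Directions for Administration): "The dose range for patients 6 to 16 years of age is 15 to 60 mg and for those 17 years and older"; the sentence then gives 30 to 80 mg daily for the older group. The same paragraph sets a 20 mg maximum single dose.
- SAP 5.3 repeats the 10.3.3 ranges and the single-dose maximum.
- Protocol Synopsis, investigational product entry: "Dosing is up to 80 mg/day in 3 or 4 divided doses". It gives neither an age band nor a lower limit.

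Three protocol passages let the Investigator change the dose:

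- Synopsis: "The Investigator may adjust the dose of amifampridine during the course of this trial".
- Section 10.1: "The Investigator may alter the dose and dosing frequency during the Long-Term Study".
- Section 10.3.3: "The daily dose of amifampridine can be adjusted during this long-term at the discretion of the Investigator".

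None of the three says that the new dose must lie in the range for the patient's age.

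Children are in scope. The 10.3.3 band starts at age 6, Protocol 10.7.1 names a paediatric quality-of-life instrument, and Protocol 13.1 requires parents' signatures for patients under 18.

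**The concern.** Two sections of one protocol answer the same question differently: what daily dose may this patient take? A child on 20 mg four times a day fits 10.3.5 and the Synopsis but is above the 10.3.3 range. An adult on 20 mg a day fits 10.3.5 but is below the 10.3.3 range.

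The primary objective is long-term safety and tolerability, and doses can be changed over up to 27 months of visits. The upper end for children is where the difference matters most. A site relying on 10.3.5 could titrate a child beyond the range in 10.3.3. A monitor could then not say from the text alone whether that dose is a protocol deviation.

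**Working it through.** The plan offers no calculation to reproduce, so the check sets the stated limits side by side. The paediatric figures in 10.3.3 are read as daily totals. The word daily is attached only to the adult figures, but a 60 mg single dose would break the 20 mg cap.

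| Source | Ages 6–16 | Ages 17 and over |
|---|---|---|
| Protocol 10.3.3, SAP 5.3 | 15–60 mg | 30–80 mg |
| Protocol 10.3.5 | 20–80 mg | 20–80 mg |
| Protocol Synopsis | up to 80 mg | up to 80 mg |

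**Ages 6–16, 10.3.5 against 10.3.3**
- Upper end: 80 − 60 = 20 mg above; 20/60 = 33%.
- Lower end: 20 − 15 = 5 mg above the child floor.

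**Ages 17 and over, 10.3.5 against 10.3.3**
- Upper end: 80 mg in both, so they agree.
- Lower end: 30 − 20 = 10 mg below the adult floor; 10/30 = 33%.

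**Could 10.3.5 be a summary of both bands?** A summary would run from the lower of the two floors to the higher of the two upper ends, which is 15–80 mg. The stated range is 20–80 mg. Its lower end is neither 15 nor 30, so it is not a summary of 10.3.3.

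**Does the single-dose cap close the gap?** With three doses a day the most a patient can take is 3 × 20 = 60 mg, which is the paediatric upper end. With four it is 4 × 20 = 80 mg. Both schedules are allowed, so the cap enforces 60 mg only on the three-dose schedule.

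**Which dose levels are affected?** SAP Listing 16.2.5.2.2 codes the daily dose in 5 mg steps. If 10.3.5 is read as bounds, the two sections differ for children at 15, 65, 70, 75 and 80 mg (five levels) and for adults at 20 and 25 mg (two levels). This count shows where the texts part. It does not estimate how often such doses would be used.

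**Does another provision settle it?**
- Carrying over the SMA-001 dose fixes only the starting dose.
- The rule in Protocol 15.7 that the SAP prevails is confined to the planned statistical analysis, so SAP 5.3 does not override 10.3.5 on dosing.
- No passage states which dosing section governs.

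**The case against.** The strongest reply is that 10.3.5 is descriptive. It calls its range usual and sits under dose selection, and the only firm limit it states, 20 mg per dose, agrees with 10.3.3. The instruction to sites is 10.3.3, which the SAP repeats. The sentence on adjustment follows the age ranges in the same paragraph, so adjustment within those ranges is the natural reading. Protocol 22.1 also binds the Investigator to the protocol, and SAP 10.13 has every deviation reviewed case by case before database lock.

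Much of this stands. It makes 10.3.3 the natural controlling text and keeps the practical risk small. It does not make 20–80 mg agree with either band, and the precedence of 10.3.3 remains an inference.

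Three stronger readings are tempting, and the documents do not support them.

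- **The Synopsis contradicts 10.3.3.** It does not. As a study-wide maximum 80 mg/day is correct; the Synopsis only omits the paediatric upper end.
- **The plan sets no dose limit for children, or lets the Investigator exceed it.** Section 10.3.3 does give a paediatric range, and no passage permits going beyond it. What is missing is an explicit statement that adjustment stays inside it.
- **Compliance is computed on the wrong denominator.** The note to SAP Listing 16.2.5.2.1 says "Number of Tablets Dispensed, Number of Tablets Used, and Treatment Duration are totals from next listing. Compliance is determined from these totals", and a reader might infer that tablets used are divided by tablets dispensed. SAP 10.10.2 and the footnote to Table 14.2.4 both define compliance as consumed over prescribed. The note also lists treatment duration, which a used-over-dispensed ratio would not need. Listing 16.2.5.2.2 holds the daily dose and dates for each box, so the prescribed count can be derived. No error is shown.

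**Conclusion.** The inconsistency is real, is confined to the protocol, and is minor. Section 10.3.5 is wrong as written: it disagrees with 10.3.3 by 20 mg (33%) at the upper end for ages 6 to 16 and at the lower end for both age groups. The Synopsis is incomplete, not wrong. The SAP agrees with 10.3.3.

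This rests on reading the paediatric range as a daily total and on taking 10.3.3 as the intended rule, because it is the administration section and the SAP repeats it. How many patients could be affected is unknown: about 12 are planned, the number of children is not stated, and the SMA-001 dosing rules are not in these documents. No endpoint, analysis set or planned summary changes. The gain is a clear upper dose for children and a clear basis for calling a dose a deviation.

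**What to change.** 1. In Protocol 10.3.5, replace the 20–80 mg range with the 10.3.3 ranges (15–60 mg/day for ages 6 to 16; 30–80 mg/day from age 17), or cross-refer to 10.3.3. Keep the 20 mg single-dose maximum.
2. In the Synopsis, add the 60 mg/day upper end for ages 6 to 16 beside the 80 mg/day maximum.
3. In 10.3.3, state that Investigator adjustment stays within the range for the patient's age.

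SAP 5.3 needs no change. The cost is a short protocol amendment. Under Protocol 15.7, an amendment that influences patient risk needs ethics committee approval before it is implemented, and the third change may fall under that rule. No new data or assessments are needed.
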